NON-INTERVENTIONAL (NI) STUDY PROTOCOL

Study information

Title	Comparing Patient-Reported Outcomes Between Rimegepant and Triptan Users with Migraine in the United States
Protocol number	C4951076
Protocol version identifier	1.0
Date	04 October 2024
Active substance	Analgesics, calcitonin gene-related peptide (CGRP) antagonists. ATC code: N02CD06
Medicinal product	Rimegepant (Nurtec 75mg ODT)
Research question and objectives	
The goal of this research is to assess patient-reported outcomes (PROs), specifically treatment satisfaction, healthcare resource use (HCRU), quality of life (QoL), work productivity loss, and migraine-specific disability of Rimegepant users, relative to triptan users, among US adults diagnosed with migraine.
 
Secondarily, a sensitivity analysis will be conducted, applying a more restrictive definition for the Rimegepant acute user cohort, to corroborate the initial set of results. Findings from these analyses may be used to inform communications with payers regarding reimbursement of Rimegepant.

Country of study	United States (US)
Author	PPD [REDACTED]
This document contains confidential information belonging to Pfizer. Except as otherwise agreed to in writing, by accepting or reviewing this document, you agree to hold this information in confidence and not copy or disclose it to others (except where required by applicable law) or use it for unauthorized purposes. In the event of any actual or suspected breach of this obligation, Pfizer must be promptly notified.	

2. LIST OF ABBREVIATIONS

Abbreviation	Definition
AAN	American Academy of Neurology
AE	Adverse event
ATT	Average treatment effect of treated
CGRP	Calcitonin gene-related peptide
ER	Emergency room
FDA	Food and Drug Administration
GCS	Global composite score
HCRU	Health care resource use
HRQoL	Health related quality of life
IEC	Independent ethics committee
IP	Internet Protocol
IPTW	Inverse probability of treatment weighting
IRB	Institutional review board
mAb	Monoclonal Antibody
MCS	Mental composite score
MIDAS	Migraine Disability Assessment Scale
NHWS	National Health and Wellness Survey
NSAID	Non-steroidal anti-inflammatory drugs
OLS	Oracle Life Sciences
OTC	Over the counter
PCS	Physical composite score
PRO	Patient-reported outcome
QoL	Quality of life

US	United States of America
WPAI-GH	Work Productivity and Activity Impairment – General Health

4. ABSTRACT

None.

5. AMENDMENTS AND UPDATES

None.

6. MILESTONES

Minimum requirements:

Milestone	Planned Date
Initiation of data analysis	05 October 2024
First draft of abstract	10 October 2024
Final abstract	15 October 2024
Completion of data analysis	20 November 2024
First draft of poster content	01 March 2025
Final poster content	15 March 2025

7. RATIONALE AND BACKGROUND

Triptans, also known as serotonin receptor agonists, are considered as a standard treatment for acute migraine and have been widely prescribed in the United States¹. A systematic review showed that standard dose (taken orally or intranasally) of triptans alleviated pain within 2 hours in 42 to 76% of patients and provided sustainable headache relief at 24 hours in 29% to 50% of patients². However, triptans are not for preventing migraine and are associated with numerous adverse events including nausea, dizziness, and coronary vasoconstriction³.

Rimegepant, an oral medication which works by blocking the calcitonin gene-related peptide (CGRP) receptors, was approved by the Food and Drugs Administration (FDA) in February 2020, as an alternative method for the acute treatment of migraine in adults⁴. Rimegepant relieves pain as well as incommodeous symptoms and can prevent migraine when given the proper dose⁵. However, nausea, urinary tract infection, and dizziness were adverse events reported for Rimegepant⁶.

Both triptans and Rimegepant are commonly prescribed for acute migraine but have different efficacy and side effects. Triptans showed better pain relief compared to gepants, whereas gepants were associated with fewer adverse events compared with triptans¹. Recent research also showed Rimegepant being more effective in the acute treatment of migraine in adults with a history of insufficient response to 1 or ≥ 2 triptans among and in current triptan users⁷.

As patients with migraine tend to experience worse health status, reduced health-related, reduced work productivity, the impact of treatment in improving patient reported outcomes is critical^{8,9}. Among triptan users, the HRQoL and work productivity were significantly impacted in those with insufficient response to triptans¹⁰. In addition to the reduction in migraine frequency, Rimegapant was associated with improvement in HRQoL over time¹¹. However, few studies have comprehensively examined patient reported outcomes among Rimegepant users compared with triptan users. As such, the purpose of this study was to assess patient-reported outcomes (PROs) including treatment satisfaction, healthcare

resource use (HCRU), quality of life (QoL), work productivity loss, and migraine-specific disability of Rimegepant users, relative to triptan users.

8. RESEARCH QUESTION AND OBJECTIVES

The primary aim of this analysis is to assess PROs, specifically treatment satisfaction, HCRU, QoL, work productivity loss, and migraine-specific disability of Rimegepant users, relative to triptan users, among US adults diagnosed with migraine.

Secondarily, a sensitivity analysis will be conducted, applying a more restrictive definition for the Rimegepant user cohort, to corroborate the initial set of results. Findings from these analyses may be used to inform communications with payers regarding reimbursement of Rimegepant.

9. RESEARCH METHODS

9.1. Study Design

This is a cross-sectional study using the 2023 US (N=75,007) National Health and Wellness Survey (NHWS) data. People who use Rimegepant will be compared with those who use triptan on treatment satisfaction, HCRU, QoL, work productivity loss, and migraine-specific disability outcomes. The cross-sectional design allows us to compare the Rimegepant vs. triptan users on multiple outcomes in a relatively quick and inexpensive way.

9.2. Setting

All data from the NHWS are reported by the respondent. NHWS participants are recruited through an existing, general-purpose (i.e., not health care-specific) web-based consumer panel via opt-in e-mails, co-registration with panel partners, e-newsletter campaigns, banner placements, and affiliate networks. All panelists explicitly agree to be a panel member, register with the panel through a unique e-mail address, and complete an in-depth demographic registration profile. A stratified random sampling procedure is implemented to ensure that the demographic composition of the final NHWS sample is representative of the general adult population in the US. In each year the NHWS is fielded, data from the International Database of the US Census Bureau are used to identify the relative proportions of adults by age, race/ethnicity, and gender; these proportions are then mimicked during the recruiting of panel members.

9.2.1. Inclusion Criteria

Patients must meet all of the following inclusion criteria to be eligible for inclusion in the study:

1. Patients who have consented to the anonymous use of their data for research purpose.
2. Aged 18 or older.
3. Self-reported a diagnosis of migraine by physician.
4. Currently on Rimegepant or triptan (via oral route) use at time of survey.

5. In addition, patients to be included in the sensitivity analysis need to meet the following criteria:

- Currently on acute Rimegepant use (<12 days using Rimegepant per month), or triptan (via oral route) use at time of survey.

9.2.2. Exclusion Criteria

Patients meeting the following criteria will not be included in the study:

1. Currently on both Rimegepant and triptan use at time of survey.

9.3. Variables

The NHWS includes self-reported data on demographics, health characteristics, disease history, and health outcomes. The Table 1 below provides further details on the specific variables that will be assessed in the study.

Table 1. Study Variables

Variable	Role	Operational Definition
Rimegepant vs. triptan use	Exposure	Current Rimegepant users (for sensitivity analysis restricted to acute Rimegepant users with <12 days use per month) vs. triptan users (no OTC, oral route only).
Outcomes: Migraine treatment use and treatment satisfaction		
Migraine medication type (drug or OTC)	Outcome	Defined as drug only, OTC only and both drug and OTC, based on current use of migraine medication classes
Migraine treatment type (acute or prevention)	Outcome	Defined as acute only, prevention only and both acute and prevention, based on current use of migraine medication classes
Total number of acute migraine agent drug (continuous)	Outcome	Total number of acute agent classes (both drug and OTC) used
Total number of acute migraine agent drug (categorical)	Outcome	Including 1 drug class, 2 or more drug classes, and 3 or more drug classes based on the total number of acute agent (both drug and OTC) classes used
Total number of prevention migraine agent drug (continuous)	Outcome	Total number of prevention agent classes (only drug) used
Total number of prevention migraine agent drug (categorical)	Outcome	Including 1 drug class, 2 or more drug classes, and 3 or more drug classes based on the total number prevention agent classes (only drug) used
Current migraine treatments (drugs)	Outcome	Defined as yes or no for current migraine treatments on drug classes including: Rimegepant, triptans, NSAIDs, opioids, barbiturates, ergots, gepants (acute, including Rimegepant), ditans, combination analgesics, other acute drugs, anticonvulsants, beta-blocker, antidepressant, CGRP mAb, botox, and gepant (prevention, including Rimegepant)
Treatment satisfaction (drugs)	Outcome	Treatment satisfaction of drug classes of: Rimegepant, all acute agents, triptans, NSAIDs, opioids, barbiturates, ergots, gepants (acute), ditans, combination analgesics, other acute treatment, all prevention agents,

		anticonvulsants, beta-blockers, antidepressants, CGRPs mAb, botox, and gepant (prevention) Categorized into 7 categories: extremely dissatisfied, very dissatisfied, somewhat dissatisfied, neither dissatisfied nor satisfied, somewhat satisfied, very satisfied, extremely satisfied
Current migraine treatments (OTC)	Outcome	Defined as yes or no for current migraine treatments on OTC classes of analgesics (acetaminophen only), analgesics (combinations), NSAIDs, other OTCs
Treatment satisfaction-analgesics (acetaminophen only)	Outcome	Treatment satisfaction of OTC classes of analgesics (acetaminophen only), analgesics (combinations), NSAIDs, and other OTCs Categorized into 7 categories: extremely dissatisfied, very dissatisfied, somewhat dissatisfied, neither dissatisfied nor satisfied, somewhat satisfied, very satisfied, extremely satisfied
Outcomes: HRQoL		
RAND-36	Outcome	PCS, MCS, and GCS index scores of the RAND-36 ¹²
EQ-5D-5L	Outcome	Health state utilities and the EuroQoL Visual Analog Scale (EQ-VAS) ¹³
WPAI-GH	Outcome	Absenteeism (% of work time missed because of one's health in the past 7 days), presenteeism (% impairment experienced while at work in the past 7 days because of one's health), overall work impairment (combination of absenteeism and presenteeism), and activity impairment (% impairment in daily activities because of one's health in the past 7 days) among total population, employed, unemployed, and disabled ¹⁴
MIDAS	Outcome	Total score, categorical (grade I-IV), and item scores (1-7) of MIDAS ¹⁵
Outcomes: HCRU		
ER visits	Outcome	Visited ER in past 6 months (yes or no); number of ER visits in past 6 months among total population and participants with ER visits
Hospitalizations	Outcome	Was hospitalized in past 6 months (yes or no); number of hospitalizations in past 6 months among total population and participants with hospitalizations
General practitioner/family practitioner visits	Outcome	Visited general practitioner/family practitioner in past 6 months (yes or no); number of general practitioner/family practitioner visits in past 6 months among total population and participants with general practitioner/family practitioner visits
Cardiologist visits	Outcome	Visited cardiologist in past 6 months (yes or no); number of cardiologist visits in past 6 months among total population and participants with cardiologist visits
Neurologist visits	Outcome	Visited neurologist in past 6 months (yes or no); number of neurologist visits in past 6 months among total population and participants with neurologist visits
Traditional healthcare provider visits	Outcome	Visited traditional healthcare provider in past 6 months (yes or no); number of traditional healthcare provider visits in past 6 months among total population and participants with traditional healthcare provider visits
Covariates adjusted through IPTW		
Age (continuous)	Potential confounder	Age of participants in years

Sex	Potential confounder	Male vs. female
Race	Potential confounder	Categorized as black, white, and other
Hispanic/Latino	Potential confounder	Yes vs. no
Marital status	Potential confounder	Single/ not living with partner vs. married/ living with partner
Health insurance	Potential confounder	Categorized as private insurance, public insurance, no insurance, and unsure
University education	Potential confounder	Less than university education vs. university education or higher
Annual household income	Potential confounder	Categorized as below median income (<50,000), median income (\$50,000-\$74,999), above median income (\geq \$75,000), and decline to answer
Employed	Potential confounder	Yes (full-time/ part-time/ self-employed) vs. no
Charlson comorbidity index	Potential confounder	Charlson comorbidity index scores with and without patients of score 0 and categories based on scores: 0, 1, 2, 3, and 4+
Body mass index	Potential confounder	Body mass index in kg/m ²
Alcohol use	Potential confounder	Currently drink alcohol vs. currently do not drink alcohol
Smoking status	Potential confounder	Categorized as current smoker, former smoker, and never smoked
Exercise	Potential confounder	Number of days exercise per months
Contraindications	Potential confounder	Ever experienced each of contraindications (angina, arrhythmia, atrial fibrillation, congestive heart failure, heart attack, left ventricular hypertrophy, mini-stroke/transient ischemia attack, peripheral arterial disease /poor circulation, Peripheral vascular disease, stroke, and unstable angina/chest pains)
Cardiovascular risk factors	Potential confounder	Ever experienced each of cardiovascular risks (high blood pressure, high cholesterol, current smoker, type 2 Diabetes, and obesity)
Any contraindications	Potential confounder	Ever experienced any contraindications listed above
Any cardiovascular risk factors	Potential confounder	Ever experienced any cardiovascular risks factors listed above
Any contraindications or cardiovascular risk factors	Potential confounder	Ever experienced any contraindications or cardiovascular risks factors listed above
Time since migraine diagnosis	Potential confounder	Time since migraine diagnosis in years
Monthly migraine days (continuous)	Potential confounder	Number of days experienced migraine in past 30 days
Monthly headache days (continuous)	Potential confounder	Number of days experienced headache in the past 30 days
Medication overuse (migraine only)	Potential confounder	Yes or no, for migraine-specific medications only
Other covariates that will be evaluated for balance between exposure groups		
Age (categorical)*	Potential confounder	Categorized based on age of participants in years: 18-29, 30-39, 40-49, 50-59, 60-69, 70-79, 80-89
Monthly migraine days (categorical)*	Potential confounder	Categorized based on number of days experienced migraine in past 30 days: <4, 4-9, 10-14, and \geq 15
Monthly headache days (categorical)*	Potential confounder	Categorized based on number of days experienced headache in past 30 days: <4, 4-9, 10-14, and \geq 15
Experience migraines related to menstrual cycle	Potential confounder	Yes vs. no, female participants only

*Categorical age, monthly migraine days, and monthly headache days will be included in inverse probability of treatment weighting (IPTW) adjustment if their distributions are not balanced (standardized mean difference >0.1) after IPTW.

Abbreviations: OTC: over the counter; NSAID: non-steroidal anti-inflammatory drugs; CGRPs mAb: calcitonin gene-related peptide antibodies monoclonal antibodies; HRQoL: health related quality of life; PCS: physical composite score; MCS: mental composite score; GCS: global composite score; WPAI-GH: the Work Productivity and Activity Impairment – General Health; MIDAS: Migraine Disability Assessment Scale; HCRU: health care resource utilization; ER: emergency room; IPTW: inverse probability of treatment weighting

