9.5. Study Size

Sample size estimates, based upon preliminary feasibility, are provided below, in Table 2. The sample size for this study is fixed by the number of patients in the NHWS database who meet the imposed criteria.

Table 2. Estimated Sample Sizes

Patient Cohorts	n
Overall NHWS sample	75,007
Diagnosed with migraine	8,439
Triptan users (oral route only, no OTC) without Rimegepant use	1,340
Rimegepant users without triptan use	144
Rimegepant users (acute only) without triptan use*	112

*For sensitivity analysis.

Abbreviations: NHWS: National Health and Wellness Survey; OTC: over the counter

A sample size of 1) 130 and 2) 100 in each group (1:1 allocation) will have 80% power to detect an effect size of at least 1) 0.35 standard deviation (SD) units (indicative of at least a “small-to-medium” effect) and 2) 0.4 SD units (indicative of a medium effect), respectively, using a 2-group t-test with a 5% 2-sided significance level. We will have a sample size much greater than 130 in one of our groups, resulting in higher statistical power compared to the 1:1 allocation mentioned above. A total sample size of 100 will have 80% power to detect an effect size from a chi-square distribution of at least 0.33 (indicative of at least a “small-to-medium” effect) using a chi-square test with a 5% 2-sided significance level and 3 degrees of freedom. There will be sufficient power to detect a “small-to-medium” effect of Rimegepant user vs. triptan use on the outcomes in the main analysis, and sufficient power to detect a medium effect in the sensitivity analysis with acute Rimegepant users only.

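### An undefined no-OTC condition is written on the triptan cohort only; read as no concurrent OTC use, it would select on a study outcome in one arm

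*Combined protocol and SAP*

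**What the plan says.** The comparator is described in three places, and they do not match.

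- **Section 9.2.1, criterion 4:** "Currently on Rimegepant or triptan (via oral route) use at time of survey". The one exclusion, in section 9.2.2, is dual use: "Currently on both Rimegepant and triptan use at time of survey". Neither section mentions OTC products, for the main or the sensitivity analysis.
- **Section 9.3, Table 1, exposure row:** "vs. triptan users (no OTC, oral route only"). The Rimegepant side of the same row reads "Current Rimegepant users (for sensitivity analysis restricted to acute Rimegepant users with <12 days use per month") and has no OTC condition.
- **Section 9.5, Table 2:** "Triptan users (oral route only, no OTC) without Rimegepant use", n = 1,340. The Rimegepant row reads "Rimegepant users without triptan use", n = 144, with 112 in the acute-only subset. Again there is no OTC condition.

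OTC use is also an outcome in Table 1. Medication type is split into drug, OTC or both. The acute-class count is "Total number of acute agent classes (both drug and OTC) used". Each OTC class has its own use indicator ("Defined as yes or no for current migraine treatments on OTC classes") and its own seven-category satisfaction rating.

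**The concern.** A triptan user who also takes an OTC analgesic is eligible under section 9.2. Under one reading of Table 1 that person is not in the cohort, while a Rimegepant user with the same habit stays in. A programmer working from section 9.2 and another working from Table 1 could therefore build different comparator cohorts.

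If the restrictive reading is applied, the study selects on one of its own outcomes in one arm. The between-arm OTC comparisons would then show how the cohort was built, not how patients behave. Section 9.7 targets the effect among Rimegepant users (ATT), so triptan users are weighted to resemble them. With OTC co-users removed from the triptan side, no triptan user could stand in for a Rimegepant user who takes OTC products. Section 8 says the results may inform payer communications, and this definition sets the comparator for every contrast.

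Route has a smaller mismatch of the same kind. A patient on both an oral and a non-oral triptan meets criterion 4 but arguably fails the oral-only wording of the two tables.

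**Working it through.** **1. The definitions side by side**

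| Place | OTC condition, triptan arm | OTC condition, Rimegepant arm | Triptan route |
|---|---|---|---|
| 9.2.1 and 9.2.2 | none | none | oral use |
| Table 1 | no OTC | none | oral only |
| Table 2 | no OTC (n = 1,340) | none (n = 144; 112 acute) | oral only |

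The condition appears in both tables, so it is not a stray slip. It is in neither eligibility section, so the cohort cannot be rebuilt from section 9.2 alone.

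**2. What each reading does to the Table 1 outcomes**

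| Outcome | Prescription triptans only | No concurrent OTC use |
|---|---|---|
| Medication type | unaffected | triptan arm 100% drug-only |
| Use of each OTC class | unaffected | triptan arm 0% |
| OTC satisfaction | unaffected | no triptan raters |
| Number of acute classes | unaffected | OTC part forced to 0; prescription part free |
| Number of preventive classes | unaffected | no OTC part in its definition |

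Under the second reading every triptan user has the value 0 for OTC use. A weighted mean of zeros is zero, so no set of weights changes the result. OTC use is not among the IPTW covariates in Table 1, and the medication-overuse covariate is limited to migraine-specific products.

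**3. How easily a structural zero becomes significant**

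Inputs are the Table 2 counts and the 5% two-sided level in section 9.7. With 0 OTC users among 1,340 triptan users and k among a Rimegepant users, the Fisher exact p-value for k = 1 or 2 is C(a, k) / C(a + 1,340, k), unweighted.

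- a = 144, k = 1: 144/1,484 = 0.097
- a = 144, k = 2: (144 × 143)/(1,484 × 1,483) = 0.009
- a = 112, k = 1: 112/1,452 = 0.077
- a = 112, k = 2: (112 × 111)/(1,452 × 1,451) = 0.006

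Two OTC users, 1.4% of 144 or 1.8% of 112, are enough to cross 0.05.

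**4. Power**

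The figures in section 9.5 reproduce, using the noncentral t and noncentral chi-square distributions:

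- 130 per group at 0.35 SD: 80.3%
- 100 per group at 0.40 SD: 80.4%
- total of 100, effect size 0.33, 3 df: 79.9%

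With the Table 2 cohorts, unweighted, the effect detectable at 80% power is 0.246 SD (144 vs 1,340) and 0.276 SD (112 vs 1,340).

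The documents do not give the share f of oral triptan users who also use OTC products. Assume 20%, 40% or 60%, and assume the 1,340 already excludes them. The unrestricted cohort is then 1,340/(1 − f):

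| f (assumed) | Triptan users | Detectable effect with 144 Rimegepant users |
|---|---|---|
| 0.2 | 1,675 | 0.243 SD |
| 0.4 | 2,233 | 0.241 SD |
| 0.6 | 3,350 | 0.238 SD |

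The Rimegepant arm limits precision, so the definition hardly affects power.

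**The case against.** The strongest reply is that the condition describes the product. It shares a bracket with the route restriction, which is about the triptan itself. A qualifier on the triptan arm alone is natural when a multi-product class is compared with a single named product. The OTC classes include an open residual category, and section 9.8 says respondents type in their OTC medications, so a triptan could be reported as OTC and a coding rule to discard it would make sense. It would also be odd to list OTC outcomes for the study and then exclude all OTC users from the larger arm. On this reading the sections agree on OTC use and nothing is fixed.

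This stands as a possible reading. A reader might infer that the product reading is ruled out because none of the named OTC classes is a triptan, but the residual category prevents that inference. The reply does not settle the matter, though. Table 1 files triptans under drugs and treats OTC as a separate category, so a no-OTC label on a triptan product would be largely redundant, while on a triptan user it has a clear meaning. The plan leaves the choice to the programmer.

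It is also fair to say that OTC use, medication type and class counts are not named in the section 8 objectives or in the section 9.7 list of weighted comparisons; of the OTC items, only OTC satisfaction plausibly falls under treatment satisfaction. All of them are nevertheless declared as outcomes in Table 1.

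**Conclusion.** The inconsistency is certain: the condition is in both tables, in neither eligibility section, on one arm only, and undefined. Its consequence depends on the reading. As prescription triptans only, no outcome is affected. As no concurrent OTC medication, three sets of outcomes (medication type, OTC class use, OTC satisfaction) are determined in the triptan arm by selection, and the acute-class count is biased downward relative to the Rimegepant arm.

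Three stronger conclusions might be inferred, and the documents do not support them.

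- **That the acute-class count is fixed too.** It is not. Triptan users can still take prescription NSAIDs, opioids, barbiturates, ergots, ditans and combination analgesics, all of which count.
- **That MIDAS, QoL and work-loss contrasts are shown to be biased.** Triptan users who need no added OTC product may be better controlled, but nothing in the plan shows it. Monthly migraine days, monthly headache days and medication overuse are IPTW covariates and may absorb part of any difference. Bias is possible and its size unknown.
- **That the cohort is really 1,675 to 3,350.** Those figures rest on assumed OTC rates and on the restrictive reading.

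This is a question of validity and reproducibility, not of power. It needs correcting because literal use of the exposure definition can generate significant results from cohort construction alone, and preventing that costs very little.

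**What to change.** 1. Use one triptan definition in section 9.2.1, Table 1 and Table 2 that does not depend on concurrent OTC use in either arm, for example: current prescription oral triptan use, with or without OTC products.
2. State once whether a patient who also uses a non-oral triptan is included.
3. Confirm that the 1,340 in Table 2 was counted under that definition, or recount it.
4. If a no-OTC population is wanted, apply it to both arms as a sensitivity analysis, drop the between-arm OTC outcomes there, and count acute classes without the OTC component.

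The cost is one edit to the cohort definition and, at most, a recount in data already held. Removing the OTC condition can only leave the triptan cohort unchanged or enlarge it, and the power statement does not need to change.

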9.7. Data Analysis

The average treatment effect of treated (ATT) will be measured to evaluate the effects of Rimegepant vs. triptan among current Rimegepant users.

Based on clinical relevance, we will prespecify a list of variables to adjust for the comparison.

Inverse probability of treatment weighting (IPTW) will be conducted to adjust for confounding by the covariates. The propensity score for each participant will be estimated by logistic regression and by including the prespecified list of variables to adjust for. Weights for ATT will be calculated for both exposed (Rimegepant users) and unexposed group (triptan users)¹⁶. Stabilized weights will be used to address extreme weight values.

To confirm that the IPTW procedure is successful, the weighted Rimegepant users and triptan users will be compared on the covariates using standardized mean difference (SMD) to ensure both groups are adequately balanced across all weighting criteria. While there is no definitive cut-off for identifying imbalance in IPTW, as a rule of thumb, a standardized mean difference (SMD) that is >0.10 is indicative of imbalance¹⁷. This threshold will be applied to determine the quality of the weighting.

Once the weighting is confirmed to be successful, bivariate analyses will be conducted to compare the weighted cohorts on treatment satisfaction, HCRU, QoL, migraine-specific

disability, and work productivity loss. Specifically, categorical variables will be analyzed using chi-square tests or Fisher's exact tests for small samples; continuous variables will be analyzed using 2-sample t-tests. Non-parametric tests may be considered for comparisons on skewed variables (e.g., HCRU) when the sample size is small (e.g., <30). For bivariate comparisons, p-values <0.05, 2-tailed, will be considered statistically significant. If there are covariates that are unbalanced after weighting (i.e., SMD >0.1), those covariates will be adjusted for in the regression analysis of outcomes. Generalized linear models will be fit depending on the distributions of outcomes.

As a sensitivity analysis, the aforementioned IPTW and bivariate comparisons will be replicated after restricting the Rimegepant user cohort to the subset of those presumed to be acute treatment users (<12 days using Rimegepant).

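### Treatment type, the prevention class count and four drug-use rows in Table 1 include the drug that defines the cohort, so they differ between cohorts even when all other treatment is the same

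*Combined protocol and SAP*

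**What the plan says.** Section 9.2.1 admits respondents who are "Currently on Rimegepant or triptan (via oral route) use at time of survey", and section 9.2.2 excludes anyone "Currently on both Rimegepant and triptan use at time of survey". The two cohorts are therefore mutually exclusive and defined by current drug use. Table 2 (section 9.5) expects 144 Rimegepant users, of whom 112 meet the acute definition, and 1,340 oral triptan users.

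Table 1 (section 9.3) then assigns the role of Outcome to:
- current use of each of 16 drug classes, among them Rimegepant, triptans, and "gepants (acute, including Rimegepant), ditans, combination analgesics, other acute drugs, anticonvulsants, beta-blocker, antidepressant, CGRP mAb, botox, and gepant (prevention, including Rimegepant";
- treatment type: "Defined as acute only, prevention only and both acute and prevention, based on current use of migraine medication classes";
- the prevention class count: "Total number of prevention agent classes (only drug) used", and a matching acute class count.

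No definition removes the index drug. Nor does the plan say whether a given Rimegepant user is counted in the acute gepant class, the prevention class, or both.

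Section 9.7 says that "bivariate analyses will be conducted to compare the weighted cohorts on treatment satisfaction, HCRU, QoL, migraine-specific" disability and work productivity loss. It sets the methods ("categorical variables will be analyzed using chi-square tests or Fisher's exact tests for small samples; continuous variables will be analyzed using 2-sample t-tests") and the threshold: "For bivariate comparisons, p-values <0.05, 2-tailed, will be considered statistically significant".

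**The concern.** A variable that contains the exposure cannot show what accompanies the exposure. In the Rimegepant and triptan rows this is plain to see. In the derived variables it is not. Section 7 notes that triptans are not preventive drugs, so an oral triptan always supplies an acute class and never a prevention class. Any Rimegepant user coded to prevention gains a prevention class and moves to prevention only or to both.

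A table reporting more prevention classes, or more use of both treatment types, among Rimegepant users would look like a difference in treatment burden. It could arise entirely from the cohort definition. Section 8 says the findings may inform communications with payers, who would want to know whether other treatment differs. Weighting does not help, because the index-drug contribution comes from cohort membership and not from a covariate imbalance.

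There is a knock-on effect for the sensitivity analysis. If coding to prevention followed the 12-day cut-off, restricting to acute users would remove the excess by construction, and the two analyses would disagree for no substantive reason.

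**Working it through.** The plan gives no figure for the treatment-use outcomes. Its power statements in section 9.5 reproduce (129 per group for 0.35 SD; 99 per group for 0.4 SD; power 0.799 for w = 0.33, N = 100, 3 df) but do not bear on this point.

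**Inputs from the documents.** n = 144 and 1,340; 144 − 112 = 32 Rimegepant users outside the acute definition; 32/144 = 0.222; two-sided alpha 0.05.

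**Assumptions, none of them in the documents.** Other treatment is identically distributed in both cohorts. The triptan effective sample size after weighting, m, is 100 to 1,340. The SD of the count of other classes, s, is 0.6 to 1.2. Use of gepants other than Rimegepant is 0 to 30%. The share on some other preventive, g, is 0.1 to 0.7.

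**1. Rimegepant row.** 144/144 against 0/1,340. For complete separation in a 2×2 table the uncorrected chi-square equals N: 144 + 1,340 = 1,484. With m = 100 it is 244, p about 5e-55. The triptan row is the mirror image if the exclusion covers every route. No assumption about other treatment is needed here.

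**2. Gepant rows.**
- Acute: if only the 112 acute users count, 112/144 = 78% against 0 to 30% gives p of 1e-13 or less.
- Prevention: if only the 32 count, with other-gepant use equal in both cohorts, p runs from about 4e-68 to 0.014. It is smaller if all 144 count.

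**3. Prevention class count.**
- Rimegepant counted in both classes: shift = 1.0 and z = 1 / [s√(1/144 + 1/m)]. With s = 1.2, m = 100: 1/0.156 = 6.4. With s = 0.6, m = 1,340: 1/0.0526 = 19.0.
- Only 32 of 144 coded to prevention: shift = 0.222. The Rimegepant variance gains 0.222 × 0.778 = 0.173, so z = 0.222 / √[(s² + 0.173)/144 + s²/m]. With s = 0.6, m = 1,340: 0.222/0.0630 = 3.53, p = 0.0004. With s = 1.2, m = 100: 0.222/0.160 = 1.39, p = 0.16. Across the grid the rejection probability is 0.28 to 0.94, where it should be 0.05.

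**4. Treatment type** (chi-square on expected tables).
- Rimegepant in both classes: all 144 fall under both, against a share g of triptan users. The largest p is about 2e-13 at m = 300 and 2e-12 at m = 100.
- 112 coded acute and 32 preventive, with 30 to 90% of the 32 also on another acute class: prevention only is impossible for a triptan user but not for these 32. The largest p is 0.014 at m = 300 or 1,340, and 0.18 at m = 100.
- All 144 coded acute and 32 also preventive: the share on both is g + 0.222(1 − g) against g. With g = 0.1 this is 0.300 against 0.100, p = 2e-12 at m = 1,340. With g = 0.7 it is 0.767 against 0.700, p = 0.095 at m = 1,340 and 0.24 at m = 100.

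**5. Acute class count.** If every Rimegepant user counts as acute, each cohort gains exactly one class and the forced difference is 0. If only 112 count, it is 112/144 − 1 = −0.22.

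**6. Not affected.** The other 12 drug rows, the OTC rows and the drug/OTC type carry no forced difference.

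**After the change.** With the index drug removed the forced difference is 0, and rejection returns to the nominal 5% when other treatment is the same.

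**The case against.** Section 9.7 names satisfaction, resource use, quality of life, disability and work productivity as the compared outcomes. Treatment use is absent there and from the aim in section 8. A reader might infer that the plan commits to testing these rows at p<0.05. The documents do not say so; it is an inference from the Outcome role and from the shared Table 1 heading for treatment use and satisfaction. That limit stands. But no section marks the rows as descriptive, and even untested, the counts and treatment type would mix index drug with other treatment.

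A reader might also infer that all of Table 1's treatment-use outcomes are compromised, or that a spurious significant result is assured. Neither holds. Twelve of 16 drug rows are clean, the acute count can cancel, and under the 32-user codings the prevention count and treatment type are not always significant. Treating those 32 as preventive is itself an assumption: Table 2 shows only that they fall outside the acute definition.

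Two further points are fair. A row labelled Rimegepant showing 144 against 0 misleads nobody. And a respondent using Rimegepant preventively is on a preventive, so a total-regimen count is accurate description. That supports tabulating totals. It does not support reading a between-cohort difference in them as a difference in other treatment.

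**Conclusion.** The point holds in limited form. Four of the 16 drug rows are fixed or largely fixed by cohort entry, and treatment type and the prevention count carry a built-in difference whenever any Rimegepant user is coded to prevention, as the wording of the prevention gepant row implies. For the prevention count the difference is +1.0 class, or about +0.22 class, depending on a coding rule the plan does not state. At +1.0 it would be detected under every assumption tried; at +0.22 it may or may not be. The acute count is affected only if some Rimegepant users are not counted as acute.

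The built-in difference follows from the definitions alone. The p-values and rejection rates rest on the assumed SDs, effective sample sizes and background treatment. RAND-36, EQ-5D-5L, WPAI-GH, MIDAS and resource use do not have this flaw, so the main aim is not threatened. The change is still worth making before results are tabulated.

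**What to change.** In Table 1:
- Show the Rimegepant and triptan rows as cohort description, without a p-value.
- Define the two gepant rows as gepants other than Rimegepant.
- For any between-cohort comparison, derive treatment type and the acute and prevention class counts from concomitant migraine treatment only, leaving out Rimegepant in one cohort and the oral triptan in the other. Give treatment type a none level and the counts a 0 level, since some respondents will have no other treatment.
- State how a non-oral triptan used alongside the oral one is counted.
- If total-regimen counts are also tabulated, label them descriptive and state which class Rimegepant is counted in.

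In section 9.7, say whether treatment use is tested or only described.

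The cost is a few lines of Table 1, a sentence in section 9.7 and a changed derivation in the R code, with no new data. The small downside is that total class counts including the index drug are no longer tested.
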